Study Protocol

Official Title: The Effect of Tele-Nursing Service on Patients' Pain and Activity Level in Patients Diagnosed With Fibromyalgia

Brief Title: The Effect of Tele-Nursing Service in Patients Diagnosed With Fibromyalgia

Unique Protocol ID: NTK

NCT Number: [NCTXXXXXXXX]

Document Date: August 18, 2025

Sponsor: Çankırı Karatekin University

Principal Investigator: Assist. [name] [name]

IRB Approval: Çankırı Karatekin University Scientific Research Ethics Committee, Approval No: 2023/09

Facility Location: Çankırı Karatekin University, [name]

Brief Summary:

The aim of the study was to determine the effect of tele-nursing service provided to patients diagnosed with fibromyalgia on the pain and activity level of patients. The study was designed as a randomised controlled experimental study in a pretest-posttest design. The research was conducted in a State Hospital between April 2024 and June 2024 with patients diagnosed with fibromyalgia who applied to the physical therapy outpatient clinic and met the inclusion criteria. The sample was divided into two groups as intervention and control groups of 22 participants by simple randomisation. Descriptive Information Form, Fibromyalgia Impact Questionnaire Revised (FIQR), McGill Pain Scale were used as data collection tools in the study. The second researcher was given the contact information of all patients and the data collection forms were applied as a pre-test. The second researcher did not know which group the patients were in. Thus, the researcher collecting the data was blinded. Data collection forms were administered by the researcher by interviewing the patient in approximately 15-20 minutes. Patients in the intervention group were called three times by phone and were trained in accordance with the prepared training booklet by first researcher.

Detailed Description:

Fibromyalgia is a chronic condition of unknown etiology, characterized by widespread musculoskeletal pain, sleep disturbances, fatigue, anxiety, and impaired cognitive functions. Fibromyalgia-related pain often increases during or after physical activity and may interfere with patients' ability to perform daily living activities. Despite extensive research, the exact cause of the disease remains unknown.

This study aimed to evaluate the effectiveness of nurse-led telephone counseling on pain severity and physical activity levels in patients who met the inclusion criteria. A total of 44 participants were enrolled: 22 in the intervention group (who received telephone-based counseling and education from a nurse) and 22 in the control group (who received no intervention).

All participants were informed about the study, and written informed consent was obtained. At baseline, all patients completed pre-test questionnaires. The intervention group received additional follow-up through two telephone calls during the intervention period.

The nurse provided education and counseling on various topics, including pain management strategies, ways to increase physical activity, appropriate exercise, and stress coping techniques. Non-pharmacological treatment options for pain relief were also discussed. The educational intervention lasted approximately 4 weeks.

Following the completion of the intervention, post-tests were administered to all participants. Two months after the intervention, the FIQR (Fibromyalgia Impact Questionnaire-Revised), and the McGill Pain Questionnaire were completed by all patients to assess outcomes.

Ethical Considerations Prior to the initiation of the study, ethical approval was obtained from the Institutional Scientific Research Ethics Committee. The study was conducted in accordance with the principles of the Declaration of Helsinki. Participants were informed that their involvement was voluntary and that they could withdraw from the study at any time without any consequences.

Statistical analysis The data were analyzed using IBM SPSS Statistics version 26.0. Group comparisons were performed using independent-samples t-tests and ANOVA. Statistical significance was set at $p<0.05$. The data were analyzed using IBM SPSS Statistics version 26.0. Group comparisons were performed using independent-samples t-tests and ANOVA. Statistical significance was set at $p<0.05$. Descriptive data were shown with mean, standard deviation, median, number and percentage. Socio-demographic differences between the intervention and control groups were analyzed using Chi-squared tests for nominal variables and independent samples t-tests for continuous variables. Paired t test was used to determine the difference between two normally distributed groups and independent t test was used for nonnormally distributed variables.

Edit Conditions

Conditions: Pain

Tele-nursing

Fibromyalgia Syndrome

Keywords: Fibromyalgia (FM)

Tele-nursing

Pain

Telehealth

Edit Study Design

Study Type: Interventional [Change...]

Primary Purpose: Prevention

Study Phase: N/A

Interventional Study Model: Parallel Assignment

The study involved two parallel groups: an intervention group receiving nurse-led telephone counseling and education, and a control group receiving no intervention. Participants were randomly assigned to each group.

Number of Arms: 2

Masking: Triple (Participant, Investigator, Outcomes Assessor)

Allocation: Randomized

Enrollment: 44 [Actual]

Open Arms and Interventions

Arms Assigned Interventions

Experimental: Intervention-telenursing

The second researcher did not know which group the patients were in. Thus, both the patient and the researcher who collected the data were blinded. the data collection forms were applied as a pre-test by second researcher. The first researcher sent an educational booklet prepared on the educational topics or the topics the patient needed to the patients in the experimental group as a message. The patient was then called by phone and informed about the educational booklet. After the main interview, the patients were called 2 more times for follow-up. The intervention group was given education on topics such as reducing pain complaints, increasing activity level, exercise, and coping with stress. The education of the intervention group lasted approximately 4 weeks. After the completion of the training of the intervention group, the second researcher applied the post-tests to all patients. The FIQR, VAS, and McGill pain scale were filled out as the post-tests.

Behavioral: Intervention-telenursing

The first researcher sent an educational booklet prepared on the educational topics or the topics the patient needed to the patients in the experimental group as a message. The patient was then called by phone and informed about the educational booklet. After the main interview, the patients were called 2 more times for follow-up. The intervention group was given education on topics such as reducing pain complaints, increasing activity level, exercise, and coping with stress. The education of the intervention group lasted approximately 4 weeks.

No Intervention: Control

The second researcher did not know which group the patients were in. Thus, both the patient and the researcher who collected the data were blinded. The second researcher was given the contact information of all patients and the data collection forms were applied as a pre-test. After the completion of the training of the intervention group, the second researcher applied the post-tests to all patients. The FIQR, VAS, and McGill pain scale were filled out as the post-tests. Participants in this group did not receive any counseling or educational intervention. They completed pre- and post-tests during the same period as the intervention group but received standard care only.

Edit Outcome Measures

Primary Outcome Measure:

1. Change in pain severity as measured by the Short Form McGill Pain Questionnaire (SF-MPQ) sensory subscale at 2 months

The Short Form McGill Pain Questionnaire (SF-MPQ) is a widely used tool for assessing the qualitative and quantitative aspects of pain. The SF-MPQ consists of three main components:

1-Pain Rating Index (PRI) — Divided into: Sensory subscale: 11 descriptors (e.g., throbbing, shooting, stabbing) Affective subscale: 4 descriptors (e.g., tiring, fearful, punishing) Each descriptor is rated on a 4-point scale: 0 = None, 1 = Mild, 2 = Moderate, 3 = Severe.

A 6-point ordinal scale where the participant selects one of the following to describe their current pain:

0 = No pain

= Mild

= Discomforting

= Distressing

= Horrible

= Excruciating Higher scores indicate more severe pain. SF-MPQ was administered at baseline and at 2 months post-intervention.

[Time Frame: At the beginning and at week 8]

Secondary Outcome Measures:

Change in health status as measured by Revised Fibromyalgia Impact Questionnaire (FIQR) at 2 months

The Revised Fibromyalgia Impact Questionnaire (FIQR) is a patient-reported outcome measure designed to assess the health status and impact of fibromyalgia on daily life. The FIQR is a revised version of the original FIQ, providing better psychometric properties and more comprehensive coverage of functional domains. The FIQR is a 21-item questionnaire measuring the impact of fibromyalgia across function, overall impact, and symptom domains. Each item is scored from 0 (no impact) to 10 (maximum impact). The total score ranges from 0 to 100, with higher scores indicating worse fibromyalgia-related health status. FIQR was administered at baseline and at 2 months post-intervention.

The FIQR consists of 21 items divided into 3 domains:

Function domain (9 items) — assesses physical functioning

Overall impact domain (2 items) — measures overall impact of fibromyalgia

Symptom domain (10 items) — evaluates common fibromyalgia symptoms (e.g., pain, fatigue, sleep quality).

[Time Frame: At the beginning and at week 8]

Other Pre-specified Outcome Measures:

Change in pain severity as measured by Visual Analog Scale (VAS) at 2 months

The Visual Analog Scale measures pain severity on a scale from 0 to 10, where 0 indicates no pain and 10 indicates the worst imaginable pain. Higher scores indicate worse pain. VAS was administered at baseline and at 2 months post-intervention.

[Time Frame: At the beginning and at week 8]

Edit Eligibility

Minimum Age: 18 Years

Maximum Age:

Sex: All

Gender Based: No

Accepts Healthy Volunteers: No

Criteria:

Inclusion Criteria:

Individuals diagnosed with fibromyalgia

Aged 18 years or older

No communication impairments that would hinder participation in the study or the ability to receive education (e.g., hearing loss, visual impairment, or difficulty understanding/speaking Turkish)

Reachable by phone

Literate

Willing to participate voluntarily.

Exclusion Criteria:

People with communication problems

People with hearing and/or speech problems

Can't speak Turkish,

Open Contacts/Locations

Central Contact Person: [name]

[contact]

Email: [contact]

Central Contact Backup: [name]

Email: [contact]

Study Officials: [name]

Study Principal Investigator

<https://karatekin.edu.tr>

Locations:

Turkey

Cankiri Karatekin University

Cankiri, Merkez, Turkey, 18200

Contact: [name] [name] [contact]

Contact: [name]

Edit IPD Sharing Statement

Plan to Share IPD: Yes

Study protocol, Informed Consent Form (ICF)

Supporting Information: Study Protocol

Informed Consent Form (ICF)

Time Frame:

for 3 years

Access Criteria:

<https://ebap.karatekin.edu.tr/?act=guest&act2=projeler&durum=tamam>

URL: <https://ebap.karatekin.edu.tr/?act=guest&act2=projeler&durum=tamam>

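### The masking field claims triple masking, but the described conduct establishes masking of one person only, the researcher who collected the data

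*Protocol*

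**What the plan says.** The protocol's Study Design section gives "Masking: Triple (Participant, Investigator, Outcomes Assessor", which is three roles.

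The narrative offers one supporting fact, in the Brief Summary and in both arm descriptions under Arms and Interventions: "The second researcher did not know which group the patients were in". The Brief Summary concludes "Thus, the researcher collecting the data was blinded". The two arm descriptions conclude "Thus, both the patient and the researcher who collected the data were blinded".

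On delivery, the Brief Summary says "Patients in the intervention group were called three times by phone and were trained in accordance with the prepared training booklet by first researcher". The experimental arm description has the first researcher send the booklet by message and then telephone the patient about it, and adds "After the main interview, the patients were called 2 more times for follow-up". Of the control arm the protocol says "Participants in this group did not receive any counseling or educational intervention", and that these patients had standard care only.

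On what patients knew, the Detailed Description says "All participants were informed about the study, and written informed consent was obtained". The SAP does not mention masking.

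**The concern.** The masking field is a headline statement of design quality. Here the text beneath it gives a reason for masking the data collector and no reason that bears on the patient. The same sentence about the second researcher leads to a narrower conclusion in one place and a wider one in two others.

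The point matters because of the outcomes. The primary outcome is the sensory subscale of the SF-MPQ, the secondary is the FIQR, and the VAS for pain is a further pre-specified measure. In each, the patient supplies the score. For such measures, masking the participant is what guards against expectation and response bias. A reader who takes the field at face value would credit the primary pain comparison with that protection.

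**Working it through.** No arithmetic beyond simple counts applies. The check sets each claimed role against the text on blinding and on delivery.

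**Outcomes assessor.** The second researcher gave the pre-tests and post-tests and is said not to have known the groups (Brief Summary and both arm descriptions). This role is supported.

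**Investigator.** The role is named only in the masking field.
- The first researcher sent the booklet and made the calls, and so knew who received the education.
- The only researcher described as masked is the second. If the field means that person, one masked individual fills two of the three roles.
- Neither the protocol nor the SAP describes a masked analyst or any other masked investigator.

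**Participant.** Patient blinding is asserted twice, once in each arm description. The reason given is what the second researcher did not know, and an interviewer's ignorance of allocation says nothing about what patients knew. The described arms give no other support:
- Intervention, 22 of 44 (22/44 = 50%): one booklet, and 1 main call + 2 follow-up calls = 3 calls, matching the three calls in the Brief Summary. These patients knew they had received education.
- Control, 22 of 44 (50%): no education contacts, and no sham or attention contact described.

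**Outcomes.** Three of three are patient ratings:
- SF-MPQ sensory subscale: 11 descriptors, each 0 to 3.
- FIQR: 21 items, each 0 to 10, described as patient-reported.
- VAS: pain from 0 to 10.

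**Mode of collection.** The Brief Summary says the researcher administered the forms by interview, in about 15 to 20 minutes. The Detailed Description says the patients completed the FIQR and the McGill questionnaire. Under either account the patient provides the answer. A masked interviewer limits prompting and differential recording, but leaves the patient's own expectations untouched.

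**Result.** Masking is established for one person. For the participant role it is asserted without a supporting reason. For the investigator role it is either a second count of the same person or undescribed.

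**The case against.** Four points can be made for the plan.

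- *The second researcher is an investigator.* The masking field does not say which investigator it means, and nothing requires investigator and assessor to be different people. This stands. A reader might infer that no masked investigator exists, or that exactly one of three roles is met; the documents do not settle either. They do show that the person delivering the intervention was not masked, and that counting one person under two roles adds no protection.
- *Receiving education is not the same as knowing the comparison.* Patients might not have been told that two groups were being compared. This also stands in part. What they were told about the arms is not in the text available, and consent pages were removed from it, so the gap is not held against the plan. A reader might infer that controls knew their allocation; the documents do not show that. The stated reason for patient blinding still fails.
- *The Brief Summary is merely silent on patients.* It does not deny that they were blinded, so the difference between sections is partly an omission. True, but the wider conclusion fails on its own terms, whatever the summary leaves out.
- *Interview by a masked researcher is a real safeguard.* It is, against interviewer influence, and the plan deserves credit for it. It does not reach patient expectation.

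An intervention of this kind is hard to mask. The open design is not the criticism; labelling it triple masked is.

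**Conclusion.** The point holds as an incorrect statement of a design property. The described conduct supports masking of the data collector. It does not support masking of participants, and it shows that the intervention provider was unmasked. The reach is the whole primary comparison: 22 of 44 patients knew they had received the education, and all three listed outcomes are patient-rated.

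A reader might go further and infer that the pain result is biased. The documents do not support that: they give nothing from which the direction or size of a bias could be derived, and none is claimed. What can be said is that the label promises a protection that the text does not show.

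The conclusion rests on two assumptions: that the arms were delivered as described, and that no masking procedure was used beyond those written down. Documentation of such a procedure would change it.

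**What to change.** 1. Change the masking field to Single (Outcomes Assessor), unless the sponsor documents how participants were masked and which investigator, other than the data collector, was masked.
2. On the same condition, in both arm descriptions replace "Thus, both the patient and the researcher who collected the data were blinded" with the Brief Summary's "Thus, the researcher collecting the data was blinded".
3. Add to the Detailed Description that the first researcher, who delivered the education, was not masked; that intervention participants were aware of the education they received; and that the comparison with standard care on self-reported outcomes may include expectation and attention effects. For controls, the sponsor should state what they were told about the study and its two groups. A remark that their masking is undocumented would be a reviewer's comment and does not belong in the protocol.

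The cost is one field, one sentence in each of two arm descriptions, and a few sentences in the Detailed Description. Enrolment of 44 is recorded as actual, so conduct cannot change, and neither the data nor the analysis is affected. The downside for the sponsor is a less favourable design label.

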Statistical Analysis Plan (SAP)

Official Title: The Effect of Tele-Nursing Service on Patients' Pain and Activity Level in Patients Diagnosed With Fibromyalgia

Unique Protocol ID: NTK

NCT Number: [NCTXXXXXXXX]

Document Date: August 18, 2025

Sponsor: Çankırı Karatekin University

Principal Investigator: Assist. [name] [name]

IRB Approval: Çankırı Karatekin University Scientific Research Ethics Committee, Approval No: 2023/09

Facility Location: Çankırı Karatekin University, [name]

Statistical analysis

The data were analyzed using IBM SPSS Statistics version 26.0. Group comparisons were performed using independent-samples t-tests and ANOVA. Statistical significance was set at $p<0.05$. The data were analyzed using IBM SPSS Statistics version 26.0. Group comparisons were performed using independent-samples t-tests and ANOVA. Statistical significance was set at $p<0.05$. Descriptive data were shown with mean, standard deviation, median, number and percentage. Socio-demographic differences between the intervention and control groups were analyzed using Chi-squared tests for nominal variables and independent samples t-tests for continuous variables. Paired t test was used to determine the difference between two normally distributed groups and independent t test was used for nonnormally distributed variables.

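### The SAP names no baseline covariate and does not say whether follow-up scores or changes were tested; state this and add a labelled post hoc baseline-adjusted ANCOVA

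*SAP*

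**What the plan says.** The SAP, Statistical analysis, describes the between-arm comparison only as "Group comparisons were performed using independent-samples t-tests and ANOVA"; the Protocol's statistics paragraph is the same. The SAP's closing sentence chooses between a paired and an independent t-test by normality, and does not say which quantity was compared. Differences between arms at entry are addressed only for socio-demographic variables.

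The Protocol's primary outcome is "Change in pain severity as measured by the Short Form McGill Pain Questionnaire (SF-MPQ) sensory subscale at 2 months". The FIQR and VAS outcomes are also titled as changes. Each scale has a baseline value: "SF-MPQ was administered at baseline and at 2 months post-intervention", "FIQR was administered at baseline and at 2 months post-intervention" and "VAS was administered at baseline and at 2 months post-intervention". The time frame attached to each outcome reads "Time Frame: At the beginning and at week 8".

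On dates, the Brief Summary says "The research was conducted in a State Hospital between April 2024 and June 2024", and the SAP title block says "Document Date: August 18, 2025".

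**The concern.** The sentence on group comparisons fits at least three analyses: a t-test on follow-up scores, a t-test on changes, and a group-by-time ANOVA. With two groups and two times, the last is equivalent to the t-test on changes. The outcome titles suggest change, but neither document connects a test to it.

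The choice matters in a trial of 44. A chance baseline difference shifts a follow-up comparison by rho times that difference, where rho is the correlation between baseline and follow-up. It shifts a change comparison by -(1-rho) times it. The two readings can therefore give different verdicts on the primary outcome, and a reader cannot tell which was used. ANCOVA with the recorded baseline removes the shift and usually narrows the interval.

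The analysed score is also not fixed in time. Education lasted about 4 weeks, so if week 8 counts from baseline, an assessment 2 months after the intervention falls at about week 12. The Protocol also describes post-tests given once the education was complete.

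**Working it through.** **Inputs from the documents.** 22 per arm (Brief Summary); significance at 0.05 (SAP); baseline and follow-up scores on all three scales (Outcome Measures). The documents give no SD, correlation, effect size or power, so there is no stated figure to reproduce.

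**Assumptions.** Two-sided test, normal scores, SD 1 at both times, no dropout, rho between 0 and 0.7. The effect is set at 0.865 SD, which gives the follow-up t-test 80% power (noncentral t, 42 df).

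**Step 1: residual variance relative to the follow-up score.** Follow-up t-test: 1. Change t-test: 2(1-rho). ANCOVA: 1-rho². At rho 0.3, 0.5 and 0.7:
- change: 1.40, 1.00, 0.60
- ANCOVA: 0.91, 0.75, 0.51

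**Step 2: power.** The noncentrality is d × sqrt(22/2) divided by the square root of the variance in step 1, with 42 df for the t-tests. ANCOVA uses 41 df, averaged over chance baseline imbalance. Full simulation with 40,000 trials per setting agrees.

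| rho | Follow-up t-test | Change t-test | ANCOVA |
|---|---|---|---|
| 0.3 | 80% | 66% | 83% |
| 0.5 | 80% | 80% | 89% |
| 0.7 | 80% | 95% | 97% |

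At rho 0, ANCOVA has 79%. It breaks even with the follow-up t-test at rho 0.16.

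**Step 3: precision at rho 0.5.** The factor (1 + 1/40) allows for estimating the slope.
- ANCOVA half-width: 2.0195 × sqrt(0.75 × 2/22 × 1.025) = 0.53 SD.
- Either t-test: 2.0181 × sqrt(2/22) = 0.61 SD.
- Equivalent size: 22 / (0.75 × 1.025) = 28.6 per arm.

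**Step 4: how often the two t-tests disagree at p<0.05** (rho 0.3/0.5/0.7).
- With the effect present: 27/23/20% of trials.
- With no effect: about 8/8/9%.
- If whichever test is significant were reported, type I error would be about 9% instead of 5%.

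**Step 5: effect of a chance baseline difference.** One standard error of the baseline difference is sqrt(2/22) = 0.30 SD. It shifts the follow-up estimate by +0.09/+0.15/+0.21 SD and the change estimate by -0.21/-0.15/-0.09 SD at rho 0.3/0.5/0.7. At this size conditional type I error is not raised (4-5%). A difference above 0.5 SD has probability 2(1 - Phi(0.5/0.3015)) = 9.7%. At exactly 0.5 SD, conditional type I error is:

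| rho | Follow-up t-test | Change t-test | ANCOVA |
|---|---|---|---|
| 0.3 | 6.5% | 11.1% | about 5% |
| 0.5 | 9.4% | 9.6% | about 5% |
| 0.7 | 13.0% | 7.7% | about 5% |

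**Step 6: non-normal scores.** The sensory subscale runs from 0 to 33 (11 descriptors × 0-3). With skewed whole-number scores (skewness 0.5, rho about 0.5), power is 78% (follow-up), 72% (change) and 87% (ANCOVA). ANCOVA's type I error is 5.1%.

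**The case against.** The Protocol calls the design pretest-posttest and titles every outcome as a change, so a change-score test is the natural reading. If that is what was run, ANCOVA gains little at high correlation: 97% against 95% power at rho 0.7. Either t-test is valid, and averaged over randomisation its type I error is 5%. The inflated errors need a 0.5 SD imbalance, and the documents report no baseline scores that show one. The 9% figure assumes that someone picked the significant test, and nothing in the documents shows this. The trial is finished, so power can no longer be planned, and a late ANCOVA adds a further p-value.

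Much of this stands, and it limits the weight of the point. The unadjusted test is not wrong, the gain depends on an unknown correlation, and the 9% describes an exposure only. It does not remove the concern. An outcome title does not say which test was run. If change was tested, saying so takes one sentence. At rho 0.3 or 0.5 the gain over a change test is 17 or 9 power points (83 against 66, 89 against 80), and a change test over-corrects for baseline differences. A labelled sensitivity analysis reported as an adjusted estimate with its interval adds very little multiplicity.

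**Conclusion.** The point holds as a recommended improvement; it does not show the analysis to be invalid. The SAP names no baseline covariate and leaves the tested quantity and the ANOVA model unstated. With 22 per arm and a true effect of 0.865 SD, that choice alone changes the significance verdict in 20-27% of trials over rho 0.3 to 0.7. Baseline adjustment shortens the interval by about 12% at rho 0.5 (0.53/0.61 = 0.87 from rounded values; 0.534/0.608 = 0.88 unrounded). It keeps type I error at about 5% whatever the baseline imbalance, and costs about 1 power point if rho is near 0. All sizes rest on assumed rho, equal SDs and no dropout. The lack of a named covariate and dependent variable rests on the documents alone.

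**What to change.** 1. For each outcome, state whether the independent t-test compared follow-up scores or changes, and which model the ANOVA was. Clarify the closing sentence on normality at the same time, since it obscures which test applied to which variable.

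2. Reconcile week 8 with 2 months after the intervention, and with the post-tests described at the end of the education. Name the one assessment that was analysed.

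3. Report the test already used first, then add text such as: *As a post hoc sensitivity analysis, the follow-up SF-MPQ sensory score was analysed by ANCOVA with arm as factor and baseline SF-MPQ sensory score as covariate; the adjusted mean difference, 95% CI and p-value are reported. FIQR and VAS were analysed in the same way, each with its own baseline. Residuals were checked, and a bootstrap CI is given beside each model-based interval.* Giving the bootstrap interval in every case avoids a data-dependent trigger.

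4. Call the ANCOVA primary only if a dated record shows that it was fixed before the data were seen. Keep within-arm paired tests descriptive.

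The cost is a few clarifying sentences, one SPSS UNIANOVA run per outcome with its bootstrap on existing data, and one degree of freedom. The SAP date of August 2025 follows the April-June 2024 conduct, so the added analysis carries post hoc weight only.

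### The statistical section chooses between a paired and an independent t test by normality; this is wrong as written and should be corrected, and the test of the primary outcome should be stated.

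*SAP*

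**What the plan says.** The section headed Statistical analysis appears with the same wording in the SAP and in the protocol's Detailed Description. Three of its sentences matter here.

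- General rule for comparing arms: "Group comparisons were performed using independent-samples t-tests and ANOVA". It names no outcome, time point or type of ANOVA, and sets no normality condition.
- Baseline characteristics: "Socio-demographic differences between the intervention and control groups were analyzed using Chi-squared tests for nominal variables and independent samples t-tests for continuous variables". This is the only sentence that ties tests to a named set of variables.
- Final sentence: "Paired t test was used to determine the difference between two normally distributed groups and independent t test was used for nonnormally distributed variables".

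The protocol's Study Design section says "The study involved two parallel groups" and "Participants were randomly assigned to each group"; it mentions no matching. The primary outcome is "Change in pain severity as measured by the Short Form McGill Pain Questionnaire (SF-MPQ) sensory subscale at 2 months", and "SF-MPQ was administered at baseline and at 2 months post-intervention". No non-parametric test is named in either document.

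**The concern.** The final sentence uses the wrong criterion. A paired test is for linked observations, such as one patient measured twice. An independent test is for separate people. Normality does not decide between them, and both tests are normal-theory procedures, so moving from one to the other does nothing for a skewed variable.

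Two readings are possible. Literally, normally distributed data from the two arms go to a paired t test, although the arms are unmatched; this contradicts the general rule in the same paragraph. Alternatively, the sentence is a garbled rule for before-after data. It then does not conflict with the general rule, but non-normal before-after data go to a test that ignores the pairing. Because both documents carry the same text, neither corrects the other.

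At stake are the validity of some within-arm results, a small loss of power if arms really were paired, and a reader's ability to tell which test lies behind each p-value.

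**Working it through.** The documents give no effect size, SD, before-after correlation or power, so there is no stated figure to reproduce. From the documents: 22 patients per arm and a 0.05 significance level. Assumed: two-sided testing, equal variances, correlation r of 0.3 to 0.7, and the effect sizes shown.

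**Literal reading: paired t across unmatched arms.** With no true linkage, both tests have the same noncentrality, d × √(n/2). For d = 0.8 this is 0.8 × √11 = 2.653. Only the degrees of freedom differ.

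| Test | df | Critical t | Power at 0.8 SD |
|---|---|---|---|
| Independent | 22 + 22 − 2 = 42 | 2.018 | 73.6% |
| Paired in arbitrary order | 22 − 1 = 21 | 2.080 | 71.6% |

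The loss is about 2 points. Simulation with normal data gives a type I error of about 5% for both tests.

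**Before-after reading: independent t on the same patients.** The variance of the mean change is 2σ²(1 − r)/n, but the independent t assumes 2σ²/n. Its standard error is therefore too large by a factor of 1/√(1 − r). A large-sample approximation to the true size is 2 × [1 − Φ(1.96/√(1 − r))]. The simulation uses n = 22 and normal scores, to isolate the effect of ignoring the pairing.

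| r | Factor | 1.96 × factor | Approximate size | Simulated size |
|---|---|---|---|---|
| 0.3 | 1.20 | 2.34 | 1.9% | 2.1% |
| 0.5 | 1.41 | 2.77 | 0.6% | 0.7% |
| 0.7 | 1.83 | 3.58 | 0.03% | 0.1% |

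Power suffers as well. For a 0.5 SD change within an arm, the independent t has 35%, 32% and 29% at these correlations, against 48%, 61% and 82% for the paired t. None of this enters the comparison between arms.

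**Does a between-arm t test need a normality switch?** The sensory score is bounded: "Sensory subscale: 11 descriptors", each rated 0 to 3, gives a range of 0 to 11 × 3 = 33. On simulated scores of this kind (skewness 0.9 or 1.7), the independent t on change has size 4.8% to 5.2%. On much more skewed raw data it is 4.6% (exponential) and 3.7% (lognormal). No switch is needed.

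**What the text implies for the primary outcome.** The outcome is defined as change, and arms are compared by independent t test or ANOVA. With two arms and two time points, one-way ANOVA on change and the group-by-time interaction are the same test as the t test on change. In a check data set t² and both F values were 6.143 on 1 and 42 df, p = 0.0173. These routes therefore agree, but no sentence says that one of them was used.

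**The case against.** The strongest reply is that little turns on this for the main result. Neither reading inflates type I error, and the second leaves the between-arm comparison alone. The general rule excludes no outcome, and together with an outcome defined as change it already leads to an independent t on change. The final sentence may be no more than a drafting or translation slip. All of this stands, and it limits the severity. It does not rescue the sentence, because a reader cannot recover from either document what was meant.

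A reader might infer more in three ways, none of which the documents support.

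- That the primary test is undetermined, with serious consequences. Independent t tests on change and on the follow-up score alone would disagree at the 5% level in 32% to 34% of trials at an assumed 0.7 SD effect. But the protocol does not define the follow-up score, or a repeated-measures group main effect, as the outcome. The rate also depends on the assumed effect: 8% to 9% at 0 SD, 12% to 17% at 0.2 SD, 28% to 40% at 0.5 SD and 1% to 6% at 1.3 SD.
- That arms were in fact compared with a paired test. The sentence permits that reading, but nothing shows it was done.
- That the test was chosen after seeing results. The documents are dated August 2025 and the study ran from April to June 2024, but they report no results and give no evidence of selection.

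**Conclusion.** The point holds as a should-fix. The rule in the final sentence is statistically wrong and stands in both documents. The cost of following it depends on the reading: about 2 points of between-arm power with size near 5%, or within-arm tests on non-normal data whose true size is about 2%, 0.7% and 0.1% instead of 5%. These figures rest on 22 per arm, two-sided 0.05, normal simulated scores, an assumed 0.8 SD effect for the power loss, and assumed correlations of 0.3, 0.5 and 0.7 for the within-arm sizes.

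The unnamed primary test is a secondary gap. The text points to an independent t on change, and one sentence would confirm it. A must-fix rating is not justified, because neither reading raises false positives or clearly damages the primary comparison.

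**What to change.** 1. State first which test actually produced each existing result. Both documents report in the past tense on a completed study, so new wording must not overwrite that record.

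2. Then replace the final sentence in both documents. Suggested text:

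> Arms are compared on change from baseline in SF-MPQ sensory score with an independent-samples t test (equivalent to the group-by-time ANOVA), whatever the normality check shows; FIQR and VAS are handled the same way. Paired t or Wilcoxon signed-rank tests describe change within an arm only and are not evidence of an intervention effect.

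The last clause is a safeguard. If both arms truly change by the same amount, a significant result in the intervention arm only arises in 12%, 25%, 24% and 18% of trials at standardised changes of 0.2, 0.4, 0.5 and 0.6, with 22 per arm.

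3. Re-run any result that came from a paired test across arms or an independent test on before-after data. Within the text, label as post hoc any analysis that differs from the one actually used.

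4. Reconcile the follow-up time before naming it in the analysis sentence. The outcome time frame says week 8, whereas the Detailed Description places assessment two months after an intervention of about 4 weeks. If the intervention began at baseline, that is roughly week 4 + 8 = 12.

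A Mann-Whitney test on change or a baseline-adjusted ANCOVA is optional and not needed to correct this error. The cost is one rewritten passage in each document, a short SPSS re-run where the wrong test was used, and a post hoc label. No new data are needed.
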